1.2 Product Development Rationale

Ipilimumab is approved for use in the US (metastatic melanoma) and in the EU (for previously treated metastatic melanoma). The currently approved dose is 3 mg/kg every 3 weeks for up to 4 doses. The current label specifies that the use of systemic corticosteroids at baseline, before starting Ipilimumab, should be avoided because of their potential interference with the pharmacodynamics and, therefore, with the efficacy of Ipilimumab. However, systemic corticosteroids or other immunosuppressants can be used after starting Ipilimumab, to treat immune-related adverse reactions. The use of systemic corticosteroids after starting Ipilimumab treatment does not appear to impair the efficacy of Ipilimumab.

Several studies have been designed that included patients with cerebral metastases. However, patients with active brain metastases with symptoms or requiring corticosteroid treatment, as well as those who had to receive concomitant radiation therapy, were almost universally excluded from these protocols. An open label phase 2 study on Ipilimumab in patients with brain metastases was recently published. However, although this trial explored the activity of the compound as a single agent for patients with or without concomitant glucocorticoids,¹ the completion of previous radiotherapy had to be done at least 2 weeks before the start of Ipilimumab.

The abscopal effect is a phenomenon in which local radiotherapy is associated with the regression of metastatic cancer at a distance from the irradiated site. The abscopal effect may be mediated by activation of the immune system. In experimental models, radiation therapy is synergistic to anti-CTLA-4 strategies.

1.2.1. Melanoma and brain metastases: clinical relevance of the condition.

Melanoma is the third most common cancer causing brain metastases, after cancers of the lung and breast,² which appears³ to reflect the relative propensity of melanoma to metastasize to the central nervous system (CNS).³ Brain metastases are responsible for 20 to 54 percent of deaths in patients with melanoma,⁴ and among those with documented brain metastases, these lesions contribute to death in up to 95 percent of cases.⁵

¹ Margolin K, Ernstoff MS, Hamid O, et al. Ipilimumab in patients with melanoma and brain metastases: an open-label, phase 2 trial. *Lancet Oncol* 2012; 13: 459–65

² Johnson JD, Young B. Demographics of brain metastasis. *Neurosurg Clin N Am.* 1996;7(3):337

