- The trial schema is represented in the following figure:

All individual patient registered into the trial should undergo the screening phase of the study. Patients consenting, registered and eligible will subsequently proceed through the treatment and follow up phases of the trial.

- **Screening Phase**

- It initiates after the written informed consent is obtained and the patients is registered. In this phase the assessment of the subject's eligibility to participate will be done, as determined by the inclusion/exclusion criteria.

- **Treatment Phase**

- Treatment will consist in the administration of ipilimumab and WBRT. The dose of ipilimumab will be 3 mg/kg, administered intravenously over a 90-minute period every 3 weeks, for a total of four doses. Standard WBRT should be initiated between the first and second dose of ipilimumab. The dose of radiation therapy will be 30 Gy over 10 fractions. Radiobiologically equivalent doses might be acceptable, but require discussion and approval of the Sponsor.
- Laboratory evaluations should be performed and the results examined before administration of each ipilimumab dose, with the exception of hormone results. For these latter parameters it is required that at least the results of the tests performed within the last 3 weeks are available and normal.
- As durable disease stabilization and/or objective tumor response can be seen after early progression before Week 12, it is recommended that, in the absence of dose-limiting toxicities

(eg, serious immune-mediated adverse reactions), all four doses of ipilimumab be administered over the initial 12 weeks even in the setting of apparent clinical progression, providing the subject's performance status remains stable.

- All subjects who enter the treatment period, including those who may have discontinued treatment for drug-related AEs and/or who have evidence of clinical progression during the induction period, should obtain a 12-week tumor assessment.
- Based on clinical experience in the ongoing and completed melanoma studies, the following recommendations apply for subject management in light of the Week 12 or later tumor assessments:

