The aim of this optional study is to determine whether a correlation between the proposed biomarkers and disease behavior (progression, overall survival, treatment response) exist in patients with melanoma metastatic to the brain, that have specifically consented for the participation in this part of the study.

The present biomarker plan proposes assessment of such biomarkers to investigate their associations with immune-mediated adverse events when ipilimumab is administered with radiation therapy:

- To evaluate tumor biomarkers pathways by IHC and their correlation with prognosis as well as their role as predictive factors to treatment with ipilimumab+radiotherapy in 29 patients participating on GEM 12-02 clinical trial.
- To evaluate serum levels of several cytoquines (by means of cytoquines panel) at baseline, and before each ipilimumab administration (expected 4-5 samples per patient, 29 patients).
- To evaluate Peripheral Blood Mononuclear Cells (PBMCs), with true counts for absolute numbers and percentage at baseline, and before each ipilimumab administration (expected 4-5 samples per patient, 29 patients).

6.4.3.b Biomarker Measures

- ALC will be assessed as a part of standard hematology panel.
- CRP will be obtained as a component of the serum chemistry lab test.
- Tumor Samples: at least 29 tumor samples (biopsies) will be collected and histology and IHC will be carried out to evaluate a panel of biomarkers that includes: CD3, CD4, CD8, CD31, PD-1, PD-L1, CD45RO, CD68, NK, DC, CD80, CD86, ICAM, VCAM, HLA-A,B,C, HLA-DR, PTEN.
- Serum Samples will be evaluated in at least 29 patients at 4-5 timepoints (116 refrigerated serum samples). For each sample, 10 ml of serum will be collected and a cytokine panel will be carried out, including:

Cytokines			
IFN- γ	TNF- α	IL-1 β	IL-2
IL-4	IL-6	IL-7	IL-8

IL-10	IL-12	IL-15	IL-17
Adhesion molecules			
sICAM-1	sVCAM-1	sCD25	

- Peripheral Blood immune cells will be evaluated in at least 29 patients at 4-5 timepoints (116 refrigerated peripheral blood samples). For each sample, 10 ml of heparin blood will be collected for flow cytometry to evaluate a panel of cells that include:

T cells			
CD3	CD4	CD8	CD56
CD45RA	CD45RO	CD62L	LFA-1 (activated conformation)
NK cells			
NKp46	CD16	CD56	
T reg			
CD4	CD25	FoxP3	
MDSC			
CD14	CD15	CD33	HLA-DR
DC			
BDCA-1	BDCA-2	BDCA-3	
T cell activation (with PMA + ionomycin)			
CD69	CD25	IFN-	IL-4
IL-17	LFA-1(active conformation)		

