9.4.5 Exploratory Analyses

Two types of ALC analyses will be done: pharmacodynamic and predictive. Both analyses will include all treated subjects with known date of first dose of ipilimumab. Pharmacodynamic analyses will examine the patterns of change in ALC over time, and how these patterns might differ between treatment arms. Predictive analyses will examine potential relationships between ALC and measures of response such as overall survival.

The proposed biomarker study includes analysis of tumor tissue at diagnosis and serum/peripheral blood at different phases within the treatment schedule. All analysed parameters will be correlated with progression-free survival (PFS), overall survival and histopathological parameters.

For the statistical analysis, it will be used binary variables, reflecting the positivity status of the measures (yes or no; presence/absence). Association with histopathological parameters. The significance level will be set at 5%. To study the impact of the histological, immunohistochemical and molecular factors on progression-free survival (PFS) and overall survival (OS), the Kaplan-Meier proportional risk test (log rank) will be used. Evidence of the relative risk for each patient will be also provided by means of a Cox proportional hazards model using stepwise selection to identify the independent predictors of poor outcome.

For the kinetic profile of the serum/blood biomarkers, each variable will be considered as continuous. A correlation at different points of the treatment schedule will be considered and the slope value will be used in order to distinguish those cases with no change, negative or positive trend. The threshold will be calculated after considering the behavior of the whole series.

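### Section 9.4.5 relates ALC and the other biomarkers to OS and PFS without adjusting for corticosteroid use at first dose, which could make an inert marker look associated with survival.

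*Protocol*

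**What the plan says.** Protocol Section 6.4.3.b states how ALC is obtained: "ALC will be assessed as a part of standard hematology panel".

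Protocol Section 9.4.5 plans two ALC analyses. The first is descriptive: "Pharmacodynamic analyses will examine the patterns of change in ALC over time, and how these patterns might differ between treatment arms". The second is "Predictive analyses will examine potential relationships between ALC and measures of response such as overall survival". On population: "Both analyses will include all treated subjects with known date of first dose of ipilimumab". No covariate is named for either.

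The same section correlates all the tissue and blood markers with PFS and OS. For histology, immunohistochemistry and molecular markers it specifies log-rank tests and a "Cox proportional hazards model using stepwise selection to identify the independent predictors of poor outcome", at a 5% level. Serial blood markers are summarised by a slope. Steroid use appears in none of this.

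Elsewhere the protocol says:

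- Section 1.2: the label advises against baseline corticosteroids "because of their potential interference with the pharmacodynamics and, therefore, with the efficacy of Ipilimumab".
- Section 4.2, exclusion 1e: only a requirement above 16 mg/day of dexamethasone, or an unstable rising dose, bars entry. Exclusion 8 removes chronic steroids given for non-cancer illness, so steroids at entry are mainly those given for the brain disease.
- Section 5.3: steroids are for symptomatic patients and not for asymptomatic ones.
- Section 3, Treatment Phase: "Standard WBRT should be initiated between the first and second dose of ipilimumab".
- Section 1.3.5.d: earlier ALC findings could not be separated from a purely prognostic association.

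The SAP tabulates steroid use and mean dexamethasone dose (Tables 7 and 8) and splits response plots by steroid use (Section 1.5.4). It lists steroids at baseline or cycle 1 as one candidate among many for 1-year OS (Table 22) and 6-month PFS (Table 32). The SAP text available contains no ALC-change analysis and no model that holds both a biomarker from Section 9.4.5 and steroid use.

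**The concern.** Steroid use at first dose is a textbook candidate confounder here. It varies between patients, it is driven by symptoms and so probably by prognosis, and the protocol itself expects it to affect what the markers are meant to measure. If it moves a marker and also tracks survival, the marker will appear related to survival even when it has no relation of its own.

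Biomarker prediction is a stated exploratory objective (Section 2.3), and Section 6.4.3.a presents such markers as possible tools for selecting patients. An association that only reflects who was on dexamethasone would mislead the next study.

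Attribution is a separate matter. Every patient receives WBRT in the early cycles, so a pattern of ALC change in this trial cannot be credited to ipilimumab alone.

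**Working it through.** **1. The plan's own figure.** The only design figure is the Fleming rule: 56 evaluable patients, success at 17 or more alive at 1 year, 20% against 35%. Exact binomial: P(X ≥ 17 | 56, 0.20) = 0.043 and P(X ≥ 17 | 56, 0.35) = 0.806. It reproduces as a one-sided design and does not involve the markers. The documents give no design figure for the biomarker analyses.

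**2. Inputs for the marker question.** From the protocol: n = 56 (Section 9.1); median OS 5.9 months for RPA class II (Section 1.2.1), used for patients off steroids; 18 months of follow-up (Section 3, study duration). Assumed, because the documents do not give them:

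- the share on steroids, p (0.3, 0.5, 0.7);
- the downward shift in the marker, δ, in within-group SD (0, 0.5, 1.0);
- the death hazard ratio for steroid users, HR (1.0, 1.5, 2.0).

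**3. Expected bias by hand.** The marker has no effect of its own. Its variance is V = 1 + p(1−p)δ². The apparent log hazard ratio per unit of marker is approximately −[δ p(1−p)/V] × ln(HR).

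- p = 0.5, δ = 1.0, HR = 2.0: −(0.25/1.25) × 0.693 = −0.139, an apparent hazard ratio of 0.87.
- p = 0.5, δ = 0.5, HR = 1.5: −(0.125/1.0625) × 0.405 = −0.048, an apparent hazard ratio of 0.95.

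In the first case the exponential survival model gives about 52 deaths among 56 patients. The SE is 1/√(52 × 1.25) = 0.124 and the shift is 0.139/0.124 = 1.12 SE. A two-sided 5% test then rejects in about 20%. In the second case (51 deaths, SE 0.135, shift 0.35 SE) it rejects in about 6%.

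**4. Simulation.** Cox model with the marker as a continuous term, 2,000 trials per setting, two-sided 5%:

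| p | δ | HR | Unadjusted | Adjusted for steroids | Apparent HR per SD, unadjusted |
|---|---|---|---|---|---|
| 0.5 | 0.5 | 1.5 | 6.2% | 5.3% | 0.96 |
| 0.5 | 0.5 | 2.0 | 9.4% | 5.6% | 0.92 |
| 0.5 | 1.0 | 1.5 | 11.1% | 6.9% | 0.91 |
| 0.5 | 1.0 | 2.0 | 17.1% | 5.8% | 0.87 |
| 0.3 | 1.0 | 2.0 | 14.1% | 5.3% | 0.89 |
| 0.7 | 1.0 | 2.0 | 15.3% | 5.2% | 0.88 |

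With δ = 0 or HR = 1.0 the unadjusted rate is 5.0-5.8%, so both links are needed. The Monte Carlo SE near 5% is √(0.05 × 0.95/2000) = 0.5 percentage points, so the mildest setting is barely distinguishable from no inflation.

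**5. Stronger assumptions.** With a median-split log-rank test, 40-60% on steroids, a shift of 1.0-1.5 SD and HR 2.0-2.5, the unadjusted rate is 13-36% at n = 56 and 9-22% at n = 29, the number planned for the tissue and serial blood markers. Stratifying by steroid use returns it to 5-6%.

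**The case against.** Much of the opposing case stands.

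- **No test is named for ALC.** Log-rank and stepwise Cox are specified for the tissue and molecular factors, and the ALC text says ALC rather than ALC change. A reader might infer that the trial plans a 5% log-rank test on ALC change with a 13-36% error rate. The documents do not support that: the rates above illustrate the size of a bias and are not the operating characteristics of a stated analysis.
- **Steroids are not ignored everywhere.** The SAP carries them as a candidate in the 1-year OS and 6-month PFS analyses. That recognises the issue for baseline characteristics but leaves the marker analyses without it, because steroid use is neither forced in nor modelled with those markers.
- **The evidence that steroids mark prognosis is thin.** Section 1.2.4 reports disease control of 12/51 (24%) off steroids and 2/21 (10%) on them. The first group was asymptomatic and the second minimally symptomatic, the outcome is not survival, and Fisher's exact p is 0.21. It is directional at best.
- **The shift is assumed.** The documents do not say that dexamethasone or WBRT lowers lymphocytes. For change scores even the direction is uncertain, since a patient already on steroids at baseline may be tapering.
- **WBRT is not a between-patient exposure.** A reader might infer that it also creates a false link between ALC and survival. Everyone receives it, so it could do so only through differences in timing or schedule. Its main effect is to prevent attribution to ipilimumab alone.
- **Adjusting for on-treatment steroid dose is debatable.** Later dosing can reflect neurological worsening or immune-related toxicity, so it conditions on post-treatment events. WBRT status also tracks time since first dose.

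What remains is narrow: a baseline variable that plausibly confounds every marker-survival analysis is missing from all of them.

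**Conclusion.** The point holds for the marker-survival analyses in Section 9.4.5. Steroid use at first dose is left out although the protocol gives its own reasons to include it. If steroids shift a marker by 0.5-1.0 SD and carry a death hazard ratio of 1.5-2.0, an inert marker is declared associated with OS in about 6-17% of trials at n = 56 instead of 5%. Adjustment restores about 5-7%. Stronger assumptions give more. If either link is absent there is no inflation. Prevalence, shift and hazard ratio are all assumptions.

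The wording on ALC patterns also needs correcting. A single-arm trial has no arms to compare, and the change seen is change under ipilimumab plus WBRT, with steroids where used.

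This is an exploratory analysis. A reader might infer that the trial's main conclusion is at risk. It is not: the primary endpoint, N = 56 and the 17-of-56 rule do not use these markers. The point is worth acting on because the correction is nearly free.

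**What to change.** In Section 9.4.5, and in the SAP if the biomarkers are reported there:

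1. Force steroid use at first dose (yes/no) and KPS into every Cox model of a marker against OS or PFS, outside the stepwise selection. Define steroid use as status at or before the first ipilimumab infusion. The SAP's baseline-or-cycle-1 variable should be checked so that it does not count steroids started later in cycle 1.
2. Stratify the log-rank tests by steroid use at first dose.
3. Name the method that relates ALC to OS, and apply the same two terms.
4. Describe ALC change as change under ipilimumab plus WBRT, with steroids where used, and delete the comparison between treatment arms.
5. Treat any model with time-varying steroid dose and WBRT status as a descriptive sensitivity analysis at most.

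Cost: wording, plus one or two degrees of freedom in a small sample, felt most in the 29-patient marker set. Concomitant medication and KPS are already collected before the first dose (Table 12), and the SAP already tabulates both steroid use and KPS, so no new data are needed.

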6.4.4. DIFFUSION-WEIGHTED MRI (DW-MRI).⁷⁰

DW Imaging (DWI) explores the random motion of water molecules in the body. Water molecules held in a container outside the body are in constant random brownian motion. This uninhibited motion of water molecules is free diffusion. By contrast, the movement of water molecules in biologic tissues is restricted because their motion is modified and limited by interactions with cell membranes and macromolecules.

In biologic tissue, the DWI signal is derived from the motion of water molecules in the extracellular space, the intracellular space, and the intravascular space. Not surprisingly, given a unit time, water molecules in the intravascular space will have a greater diffusion distance because of blood flow than those in the extracellular and intracellular spaces. Clearly, the contribution of intravascular water diffusion to the measured DWI signal can vary among tissues. In tumors showing increased vascularity, the contribution of intravascular water diffusion to the MR signal may account for a significant proportion.

The degree of restriction to water diffusion in biologic tissue is inversely correlated to the tissue cellularity and the integrity of cell membranes. The motion of water molecules is more restricted in tissues with a high cellular density associated with numerous intact cell membranes (e.g., tumor tissue). The lipophilic cell membranes act as barriers to motion of water molecules in both the extracellular and intracellular spaces. By contrast, in areas of low cellularity or where the cellular membrane has been breached, the motion of water molecules is less restricted. A less cellular environment provides a larger extracellular space for diffusion of water molecules, and these molecules may also freely transgress defective cell membranes to move from the extracellular into the intracellular compartment.

DWI yields qualitative and quantitative information that provides unique insight into tumor characteristics, and there is growing evidence for its use in the assessment of the patient with cancer.

Tumors are frequently more cellular than the tissue from which they originate and thus appear to be of relatively high signal intensity (restricted diffusion) at DWI. Tumors differ in their cellularity, and this difference may reflect their histologic composition and biologic aggressiveness. The use of DWI for tumor characterization was first shown in brain tumors.

⁷⁰ Provenzale JM, Mukundan S,P. Barboriak DP. Diffusion-weighted and Perfusion MR Imaging for Brain Tumor Characterization and Assessment of Treatment Response. Radiology 2006; 239: 632-649

Perhaps one of the most exciting potential applications of DW MRI imaging has been in measurement of the response of solid tumors to therapy. The results of several studies, usually of animal models, have suggested that substantial changes in water diffusion evolving in the first few weeks after initiation of treatment may be helpful in predicting response to therapy. If this application is validated in human studies, it could lead to important changes in clinical practice by allowing much earlier changes in therapy.

Studies of patients with brain tumors have shown that increases in water diffusion generally indicate a positive response to therapy. It appears likely, at least for some antineoplastic agents, that measurement of tumoral ADC shortly after the start of therapy might be an early marker of good response to therapy.

DW-MRI will be optional and will be done in two timepoints: at baseline (up to 2 weeks prior to therapy) and 1 month after the end of WBRT.

7. INVESTIGATIONAL PRODUCT: IPILIMUMAB

The investigational product is defined as a pharmaceutical form of an active ingredient being tested as a reference in the study, whether blinded or unblinded. In this study, the investigational product is ipilimumab.

Other medications used in the study as support or escape medication for preventative, diagnostic, or therapeutic reasons, as components of the standard of care for a given diagnosis, are considered noninvestigational products. In this protocol, a noninvestigational product is dexamethasone or equivalent glucocorticoid.

7.1. Identification

Ipilimumab is available in concentrations of 5 mg/mL (50 mg/10 mL and 200 mg/40 mL). The sterile solution in the vial is clear and colorless. Ipilimumab is administered via intravenous infusion only.

7.2. Packaging and Labeling

The Sponsor will provide ipilimumab at no cost for this study. Ipilimumab will be provided in open-label containers. The labels will contain the protocol prefix, batch number, content, storage conditions, and dispensing instructions along with the Investigational New Drug (IND) caution statement.

7.3. Storage, Handling, and Dispensing

7.3.1. Storage

Ipilimumab must be stored in a secure area according to local regulations. The investigator must ensure that it is stored at a temperature $\geq 2^{\circ}\text{C}$ and $\leq 8^{\circ}\text{C}$.

7.3.2. Handling and Disposal

As with all injectable drugs, care should be taken when handling and preparing ipilimumab. Whenever possible, ipilimumab should be prepared in a laminar flow hood or safety cabinet using standard precautions for the safe handling of intravenous agents applying aseptic technique. Latex gloves are required. If ipilimumab concentrate or solution comes in contact with skin or mucosa, immediately and thoroughly wash with soap and water. After final drug reconciliation, unused ipilimumab solution should be disposed at the site following procedures for the disposal of anticancer drugs.

